4.8 Complete System Explants

If the subject has the entire ICD system removed at any time during the study, and the subject will not receive a replacement St. Jude Medical™ MR Conditional ICD System, follow the subject for 30 days, and withdraw the subject from the study. Complete a Product Out of Service CRF and submit through EDC. A System Revision CRF is not required to be submitted.

4.9 System Revisions

In cases where only the device pocket is revised (leads are not repositioned, leads have not been disconnected from the ICD), a System Revision CRF is not required to be submitted. A System Revision CRF should be completed for all other types of revisions such as pulse generator replacement, lead replacement and lead repositioning. The subject's follow up schedule is not affected in any way.

A system revision is defined as a replacement of or repositioning of one or more components of the study ICD system (ventricular lead, compatible ICD) that occurs after the subject has been consented into the study. Because all components of the study ICD system are market-released, all procedures related to the revision should be performed according to standard of care. The revision may be performed by either a study investigator or other clinician qualified to perform such procedures.

Any explanted devices or leads (including damaged leads, lead segments and lead fragments) should be returned to St. Jude Medical promptly for analysis. Document any change to the status of the lead and device (e.g. capped, removed) on the Product Out of Service CRF.

Refer to **Table-1 Specific Study Procedures and Data Collection** to determine which case report forms need to be completed and submitted.

4.10 Description of activities performed by Sponsor Representatives

Trained sponsor personnel may perform certain activities to ensure compliance to the clinical investigational plan and may provide technical expertise. Sponsor field clinical engineers may perform the following activities:

- Interrogation of and testing the implanted ICD system at any study visit (scheduled or unscheduled): capture threshold, sensing amplitude, pacing impedance and high voltage lead impedance measurements,
- Verifying MRI scan parameters on the programmer at the MRI Scan Visit,
- Programming of the ICD per protocol, and/or as directed by the investigator/designee.

**Clinical Investigation Plan**

While sponsor representatives may perform these activities, the principal investigator remains responsible for ensuring all study data is collected as required per protocol. Deviations resulting from failure to comply with protocol requirements will be reported through completion of a Deviation CRF.

4.11 Subject Study Completion

The minimum duration of each subject's participation is approximately one month from the MRI scan (1 Month Post Scan visit). When the subject's participation in the clinical study has been completed the subject will return to standard medical care as per physician's recommendation.

4.12 Subject Withdrawal

Subjects must be informed about their right to withdraw from the clinical investigation at any time and for any reason without sanction, penalty or loss of benefits to which the subject is otherwise entitled. Withdrawal from the clinical investigation will not jeopardize their future medical care or relationship with the investigator. Subjects will be requested to specify the reason for the request to withdraw. The investigator must make all reasonable efforts to retain the subject in the clinical investigation until completion of the clinical investigation.

The investigator may decide to withdraw a subject from the clinical investigation at any time if participation is no longer medically appropriate or due to other rationale. The subject's future care will not be influenced by this decision.

Reasons for subject's withdrawal include, but are not limited to::

- Subject and/or Family Request Withdraw Consent
- Subject Lost to Follow-up
- System Explant with no system replacement (i.e. with another Durata or Optisure lead and Ellipse ICD) →Please complete a Product Out of Service Form
- Subject Death → Please complete Death, Product Out Of Service and an Adverse Event Form
- Subject Non-compliance
- Other

If a subject withdraws from the clinical investigation, the site will record reasons for withdrawal, on a Withdrawal CRF.

The status of the subject's condition should be documented at the time of withdrawal.

**Clinical Investigation Plan****4.13 Requirements for Clinical Laboratories**

Participating center should have a certified MRI laboratory & radiologist. To full fill the CIP requirement, center should be equipped with both 1.5 (For Phase 1) and 3.0 Tesla (For Phase 2) or have an associated Laboratory with required study set-up.

4.14 Study Committees**4.14.1 Steering committee**

The Steering Committee will be used to advise the Sponsor during a clinical investigation, such as in the development of the CIP, during the conduct of the study, during data analysis and/or presentation/publication of the clinical investigation results. Membership may include site investigators for the clinical investigation under review.

5 Statistical Considerations

The following section describes the statistical methods for the clinical investigation and justification of the design.

5.1 Primary Endpoint**5.1.1 Primary Endpoint and Hypothesis**

The primary endpoint is the Freedom from MRI scan-related complications related to St. Jude Medical™ MR Conditional ICD System from MRI scan to 1 month post MRI scan

Hypothesis

The hypothesis is formally expressed as:

$$H_0: P_{MRI-Scan} \leq 90\%$$

$$H_a: P_{MRI-Scan} > 90\%$$

Where $P_{MRI-Scan}$ is the freedom from MRI scan-related complications(s) related to St. Jude Medical™ MR Conditional ICD System from MRI scan to 1 month post-MRI scan visit.

The hypothesis will be tested at the 2.5% significance level. The null hypothesis will be rejected if the 97.5% lower confidence bound (LCB) for $P_{MRI-Scan}$ is greater than 90%.

5.1.1.1 Analysis Methodology

The freedom from MRI scan related complications for the SJM MR Conditional ICD system from MRI scan to 1 month Post MRI scan will be estimated using binomial proportion. The 97.5% lower confidence

**Clinical Investigation Plan**

bound will be calculated by the exact (Clopper-Pearson) method for binomial probabilities. The primary endpoint analysis will be performed for each study phase separately.

5.1.1.2 Sample Size Determination

[REDACTED]

5.1.1.3 Analysis Populations

The analysis will be conducted on subjects who meet all of the following criteria:

- Implanted with the SJM MR Conditional ICD system
- Sign informed consent
- Meet the MRI Conditions of Use
- Undergo a MRI scan
- Have 1 month post MRI scan visit or have MRI-scan related complication(s) related to SJM MR Conditional ICD system before the 1 month post MRI scan visit

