3.3 Endpoints

3.3.1 Primary Endpoint

Freedom from MRI-scan related complications* related to St. Jude Medical™ MR Conditional ICD System from MRI scan visit to 1 month post-MRI scan visit

**A complication is a serious adverse device effect (SADE) that requires an invasive intervention or leads to death.*

The primary endpoint analysis will be performed for each study phase separately.

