One Month Post- MRI Scan Visit	30 days post MRI scan (- 7/+14 days)	
• Interrogate device• Obtain in-clinic lead measurements: ventricular bipolar capture threshold, ventricular sensing amplitude, ventricular pacing impedance and high voltage lead impedance*#• Evaluate subject Adverse Device Effect (ADE) and Serious Adverse Device Effect (SADE), and submit an AE CRF (as applicable).• Report deviations, death, withdrawal and out of service as applicable• Upload device session record (X-file) through the EDC study site portal	
• Follow Up CRF• Device session records (X-Files) 
If applicable:
 
• AE CRF• Deviation CRF• Death CRF• Withdrawal CRF• Product Out of Service CRF
Unscheduled (if applicable)	Any time after Enrollment visit (where the subject is seen in clinic due to an ADE, SADE)	
• Interrogate device• Obtain in-clinic lead measurements: ventricular bipolar capture threshold, ventricular sensing amplitude, ventricular	
• Follow Up CRF• Device session records (X-Files)• AE CRF

Clinical Investigation Plan

Study Visit	Visit Window	Study Procedures & Data Collection	Forms and CRFs
		
pacing impedance and high voltage lead impedance*#
 
• Evaluate subject Adverse Device Effect (ADE) and Serious Adverse Device Effect (SADE), and submit an AE CRF (as applicable).• Report deviations, death, withdrawal and out of service as applicable• Upload device session record (X-file) through the EDC study site portal	
If applicable:
 
• Deviation CRF• Death CRF• Withdrawal CRF• Product Out of Service CRF

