5.1.1.5 Missing Data

The primary endpoint will be evaluated with data available. No imputations are planned for missing data for primary endpoint.

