5.2 Descriptive Endpoints

- Demographics and medical/surgical history such as gender, age, history of smoking, cardiac disease history, arrhythmia history, and indication for ICD implant, etc. Continuous variables will be summarized as sample size, mean, standard deviation, minimum and maximum. For categorical variables, the counts and percentages of subjects will be summarized for each category.
- Proportion of SJM high voltage lead implanted with SJM MR Conditional ICD with capture threshold increase of $\leq 0.5V$ @ 0.5ms from pre-MRI scan testing to 1 month post-MRI scan testing.
This proportion will be calculated as number of subjects who had high voltage lead with

[REDACTED]

Clinical Investigation Plan

capture threshold increased of $\leq 0.5V$ @ 0.5ms from pre-MRI scan testing to 1 month post-MRI scan testing divided by total number of subjects who had high voltage lead implanted, undergo a MRI scan and with both pre-MRI scan and 1 months Post MRI scan capture threshold available.

- Proportion of SJM high voltage lead implanted with SJM MR Conditional ICD with sensing amplitude decrease of $\leq 50\%$ from pre-MRI scan testing to 1 month post-MRI scan testing. This proportion will be calculated as number of subjects who had high voltage lead with sensing amplitude decrease of $\leq 50\%$ from pre-MRI scan testing to 1 month post-MRI scan testing divided by total number of subjects who had high voltage lead implanted, undergo a MRI scan and with both pre-MRI scan and 1 months Post MRI scan sensing amplitude available.
- Average and Peak Specific Absorption Rate (SAR) during MRI scan, MRI visit duration in MRI laboratory and total MRI scan duration in MRI laboratory
Average and Peak Specific Absorption Rate (SAR) during MRI scan, MRI visit duration in MRI laboratory and total MRI scan duration in MRI laboratory will be summarized as mean, standard deviation, minimum, median and maximum.
- Adverse events and death
The number of events, number of subjects who encountered the events will be summarized for each event category for ADE and SADE separately. The number of death will be summarized as counts and percentages for each primary cause.

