**Clinical Investigation Plan**

The safety surveillance and the safety reporting will continue until the last investigational visit has been performed, the subject is deceased, the subject/investigator concludes his participation into the clinical investigation or the subject withdrawal from the clinical investigation.

All Adverse Device Effects (serious or non-serious) are to be documented and reported to the sponsor as soon as possible after becoming aware of the event.

Adverse Event (AE)

Any untoward medical occurrence, unintended disease or injury, or untoward clinical signs (including abnormal laboratory findings) in subjects, users or other persons, whether or not related to the investigational medical device under clinical investigation.

This definition includes events related to the investigational medical device or the comparator.

This definition includes events related to the procedures involved.

Serious Adverse Event (SAE)

An adverse event that led to:

- Death
- A serious deterioration in the health of the subject, that either resulted in:
 - A life-threatening illness or injury OR
 - A permanent impairment to a body structure or a body function OR
 - An in-patient or prolonged hospitalization OR
 - A medical or surgical intervention to prevent life-threatening illness or injury or permanent impairment to a body structure or a body function OR
- Fetal distress, fetal death or a congenital abnormality or birth defect

A planned hospitalization for a pre-existing condition, or a procedure required by the CIP is not considered a serious adverse event.

Adverse Device Effect (ADE)

An adverse event related to the use of an investigational medical device.

This definition includes adverse events resulting from insufficient or inadequate instructions for use, deployment, implantation, installation, or operation, or any malfunction of the investigational medical device.

This definition includes any event resulting from the use error or from intentional misuse of the investigational medical device.

Serious Adverse Device Effect (SADE)

Adverse device effect that has resulted in any of the consequences characteristic of a serious adverse event.

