8.2.1 Subject Death

All subject deaths are to be documented and reported to the Sponsor as soon as possible and as per local laws and regulations) after becoming aware of the event.

Should death occur, the investigator is requested to record death information in the hospital records and immediately document the information on the Death form. By completing the form the sponsor will be notified.

In case of EDC failure, notify Sponsor via [contact] or via Fax (please refer to the Investigator Site Binder, for further details about Fax numbers).

Patient Death can be an outcome of a serious adverse event (SAE).

- All efforts to obtain the details should be made and the Adverse Event form must be completed.
- The patient's death is an Early Conclusion of the subject's participation in the investigation. Therefore, the investigator is requested to complete the Termination form.

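### The primary analysis set drops a scanned subject who dies before the 1-month visit unless the death is classed as a related complication, and the plan has no rule for deaths of undetermined cause

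*Combined protocol and SAP*

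**What the plan says.** Section 5.1.1.3 opens with "The analysis will be conducted on subjects who meet all of the following criteria", so every listed criterion must hold. The last one asks that the subject "Have 1 month post MRI scan visit or have MRI-scan related complication(s) related to SJM MR Conditional ICD system before the 1 month" post-scan visit.

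The failure event is set in 3.3.1: "A complication is a serious adverse device effect (SADE) that requires an invasive intervention or leads to death". Section 8.2 and Appendix B define an adverse device effect as "An adverse event related to the use of an investigational medical device". A death is therefore a primary failure only if it has been classed as device-related, and the endpoint also requires a relation to the scan.

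Section 8.2.1 states that "death is an Early Conclusion of the subject's participation in the investigation", so a subject who dies first cannot have the visit. Section 5.1.1.5 adds "No imputations are planned for missing data for primary endpoint", and no sensitivity analysis is planned. In 5.2, deaths are handled descriptively: "The number of death will be summarized as counts and percentages for each primary cause".

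The only committee described is the Steering Committee (4.14.1). It is advisory and may include site investigators. Nothing in the plan gives it the task of classifying deaths.

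**The concern.** The rule makes entry to the only hypothesis test depend on surviving to the visit or on having an event judged related. That judgement is hardest to make for a sudden or unwitnessed death. The plan's own risk list (7.1, Table 5) includes damage that leaves the system unable to detect or treat an arrhythmia, ventricular tachycardia or fibrillation, thrombus or embolism from lead heating, and pulmonary embolism. Each of these could present as a sudden death in this population, so exclusion of such a death need not be neutral.

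Section 5.6 says that safety is established for a phase if the primary endpoint is met. The estimate behind that statement could exclude a post-scan death whose cause was never settled. If the handling is decided only after a death has occurred, the choice will be hard to defend whichever way it goes.

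**Working it through.** **Tracing the rule.** Take a scanned subject who meets the other criteria in 5.1.1.3.

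- Dies before the visit, death classed as a scan- and system-related complication: enters by the second condition and counts as a failure.
- Dies before the visit, death classed as unrelated: meets neither condition and is excluded.
- Dies before the visit, relation undetermined: the text gives no rule. The subject is a failure if classed as related and is excluded otherwise.
- Attends the visit and dies later: stays in the set, so the rule does not affect this case. The visit window is day 23 to day 44 (30 − 7 and 30 + 14).

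**Inputs.** The performance goal is 90%, tested at 2.5% with an exact Clopper-Pearson 97.5% lower bound (5.1.1, 5.1.1.1). Data are frozen for each phase at 168 completed 1-month visits (5.6), and 198 are enrolled per phase (5.5). The sample-size section is redacted, so its derivation cannot be reproduced. As a consistency check, 168/(1 − 0.15) = 197.6, which rounds up to 198 if 15% attrition is assumed. I take 168 as the evaluable number before any death is added back.

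**Formula.** For f failures in n, the bound is the 2.5% quantile of Beta(n − f, f + 1). With f = 0 this is 0.025^(1/n).

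**Decision limit at n = 168.** With 9 failures the bound is 90.07% (goal met); with 10 it is 89.33% (missed). The exact type I error at a true rate of 90% is P(at most 9 failures) = 0.0233.

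**Adding d excluded deaths back as failures**, so that failures become f + d and n becomes 168 + d:

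| Known complications f | Bound, deaths excluded | Largest d that still meets the goal | Smallest d that misses it |
|---|---|---|---|
| 0 | 97.83% | 9 (9/177: 90.57%) | 10 (10/178: 89.91%) |
| 6 | 92.39% | 3 (9/171: 90.24%) | 4 (10/172: 89.57%) |
| 8 | 90.83% | 1 (9/169: 90.13%) | 2 (10/170: 89.45%) |
| 9 | 90.07% | 0 | 1 (10/169: 89.39%) |

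With f = 0 and d = 1, the bound is 96.75% (1/169).

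**Direction.** If the excluded death was truly unrelated, the rule removes a success, and keeping the subject raises the bound slightly: 0/168 gives 97.83% and 0/169 gives 97.84%; 9/168 gives 90.07% and 9/169 gives 90.13%. Exclusion is favourable only when the death was truly related.

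**How often a death might occur.** The documents give no mortality figure. If 1-month all-cause mortality is assumed to be 0.3% to 1%, the expected deaths among 168 are 168 × 0.003 = 0.5 to 168 × 0.01 = 1.7. The chance of at least one, 1 − (1 − m)^168, is 40% to 82%. Only deaths of undetermined relation raise the classification question, and the documents give no basis for estimating that fraction.

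**The case against.** The strongest reply has four parts.

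1. **The text does not force exclusion of an unexplained death.** If the death is classed as a serious device effect related to scan and system, it is a complication and enters as a failure. A reader might infer that every death of unknown cause drops out automatically. The documents do not say so; they leave the matter open. This part stands, and it is why the point concerns an unspecified rule for those deaths. Exclusion is certain only for deaths classed as not related.

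2. **Deaths are neither hidden nor beyond later clarification.** Section 8.2.1 requires every death to be documented, with efforts to obtain details and an adverse event form. Section 4.12 adds death and product out-of-service forms, 4.9 asks for explanted hardware to be returned for analysis, and 5.2 reports deaths by cause. A reader might infer that a phase could report complete freedom from complications with a death out of sight. These sections do not support that. The death is missing from the primary estimate but not from the report.

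3. **The decision is rarely sensitive.** A reader might infer that one death could overturn the result in general. That holds only with exactly 9 complications among 168. Section 3.4.2 also excludes subjects with a life expectancy under 12 months.

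4. **Making every undetermined death a primary failure would change the endpoint.** It would add background mortality to a relatedness-based, single-arm comparison with a fixed goal. This is a fair reason to leave that step to a sensitivity analysis.

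The same criterion also drops scanned subjects who withdraw or are lost before the visit. Death differs because the missing visit can never be made up and because death is itself part of the endpoint.

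**Conclusion.** The concern holds as a defect in the analysis-set rule. Deaths before the 1-month visit that are not classed as related are removed from the primary analysis. For undetermined deaths the outcome depends on a call with no default and no described independent adjudication.

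The size is modest. With no complications the bound loses about 1.1 percentage points for one death counted as a failure (97.83% − 96.75% = 1.08), and the goal is still met comfortably. The conclusion becomes fragile only when complications are already close to 9 in 168. The documents do not support a claim that the rule always favours the device, since dropping a truly unrelated death lowers the bound slightly.

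These figures assume 168 evaluable subjects per phase before deaths are added, and they treat each added death as a failure, which is the worst case. The change should be made, but the finding does not by itself put the design in doubt.

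**What to change.** - In 5.1.1.3, extend the last criterion so that every scanned subject who dies before the 1-month visit stays in the analysis set. Count deaths classed as related to scan and system as failures, and deaths with a documented unrelated cause as complication-free.
- Before data are seen, state how deaths of undetermined relatedness are classified in the primary analysis, who makes that classification, and on what information.
- Beside the primary result for each phase, report a sensitivity analysis that counts undetermined deaths as failures, and then one that counts all deaths from scan to 1 month as failures.

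The cost is SAP wording and one or two extra result lines per phase. No added visits, procedures or subjects are needed. The reported rate may be slightly less favourable.

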5.1.1.4 Subgroup Analysis

There are no subgroup analyses planned for this study.

5.1.1.5 Missing Data

The primary endpoint will be evaluated with data available. No imputations are planned for missing data for primary endpoint.

5.2 Descriptive Endpoints

- Demographics and medical/surgical history such as gender, age, history of smoking, cardiac disease history, arrhythmia history, and indication for ICD implant, etc. Continuous variables will be summarized as sample size, mean, standard deviation, minimum and maximum. For categorical variables, the counts and percentages of subjects will be summarized for each category.
- Proportion of SJM high voltage lead implanted with SJM MR Conditional ICD with capture threshold increase of $\leq 0.5V$ @ 0.5ms from pre-MRI scan testing to 1 month post-MRI scan testing.
This proportion will be calculated as number of subjects who had high voltage lead with

[REDACTED]

Clinical Investigation Plan

capture threshold increased of $\leq 0.5V$ @ 0.5ms from pre-MRI scan testing to 1 month post-MRI scan testing divided by total number of subjects who had high voltage lead implanted, undergo a MRI scan and with both pre-MRI scan and 1 months Post MRI scan capture threshold available.

- Proportion of SJM high voltage lead implanted with SJM MR Conditional ICD with sensing amplitude decrease of $\leq 50\%$ from pre-MRI scan testing to 1 month post-MRI scan testing. This proportion will be calculated as number of subjects who had high voltage lead with sensing amplitude decrease of $\leq 50\%$ from pre-MRI scan testing to 1 month post-MRI scan testing divided by total number of subjects who had high voltage lead implanted, undergo a MRI scan and with both pre-MRI scan and 1 months Post MRI scan sensing amplitude available.
- Average and Peak Specific Absorption Rate (SAR) during MRI scan, MRI visit duration in MRI laboratory and total MRI scan duration in MRI laboratory
Average and Peak Specific Absorption Rate (SAR) during MRI scan, MRI visit duration in MRI laboratory and total MRI scan duration in MRI laboratory will be summarized as mean, standard deviation, minimum, median and maximum.
- Adverse events and death
The number of events, number of subjects who encountered the events will be summarized for each event category for ADE and SADE separately. The number of death will be summarized as counts and percentages for each primary cause.

